8.4.1 Escalation Design

CONFIDENTIAL

This material is the property of the study sponsor. Do not disclose or use except as authorized in writing by the study sponsor

Printed on 1/31/2017

Because of the successful outcome with 2 and 3 fractions of SBRT in the University of Pennsylvania Phase 1 trial, the initial dose level in this study will be Dose level 1 (3 fractions of SBRT).

Dose level 1. This trial will begin enrolling at dose level 1, 3 fractions of SBRT, which has been shown to be safe in the Phase 1 trial at University of Pennsylvania. However, if one DLT has been observed in any patient, then all remaining patients must be followed for 30 days after the 4th or final injection. Two or more DLTs will cause de-escalation to Dose level -1, which will be the MTD.

Dose level -1. If two or more DLTs are observed in Dose Level 1, then all subsequent patients will be treated at Dose Level -1. If DLTs are observed at dose level -1, this will cause termination of the study.

Replacement of patients: Subjects/patients who discontinue from the study for reasons unrelated to the study (e.g. personal reasons or adverse events after registration but prior to receiving study therapy) may be replaced as required for the study to meet its objectives. Patients that have received study therapy, but who withdraw for reasons unrelated to toxicity prior to the required observation period to determine absence of DLT, will not count toward dose escalation rules and may be replaced as required. The decision to remove a subject/patient and to replace dropouts will be made by the principal investigator. The replacement will receive the same treatment or treatment sequence (as appropriate) as the allocation number replaced.

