Statistical Methodology	This is a stratified phase II study of escalating fractions of stereotactic body radiotherapy (SBRT) combined with immunotherapy for previously untreated or previously treated metastatic melanoma patients. Phase I was stratified by site: bone or lung vs. liver or s.c. Six patients were enrolled per dose cohort. Phase II is stratified by site: bone or lung vs. liver or s.c. In phase II, 20 patients will be treated at the MTD in each stratum. Descriptive statistics will be generated for both phases of the study.

CONFIDENTIAL

This material is the property of the sponsor. Do not disclose or use except as authorized in writing by the study sponsor

Printed on 1/31/2017

1 Introduction

This document is a protocol for a human research study. This study is to be conducted according to US and international standards of Good Clinical Practice (FDA Title 21 part 312 and International Conference on Harmonization guidelines), applicable government regulations and Institutional research policies and procedures.

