6.2.3 Dose fractionation and specification

The prescription dose per fraction to the PTV will be 8 Gy per fraction for a bone or lung index lesion and 6Gy per fraction for any liver or subcutaneous index lesion.

The total dose for dose level 1 (our starting dose level) will be one will be 24Gy over 3 fractions for a bone or lung index lesion and 18Gy over three fractions for any liver or subcutaneous index lesion.

If we encounter a dose limiting toxicity, we will then reduce our total dose to dose level -1. The total dose for dose level -1 will be 16Gy over 2 fractions for a bone or lung index lesion and 12Gy over two fractions for any liver or subcutaneous index lesion.

Dose rate: For the purpose of this study, dose rate utilized will be that which is commissioned by the manufacturer and the medical physics group for external beam radiotherapy delivery by the University of Washington Department of Radiation Oncology. There will be no special dose rate modifications required for this study.

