8.1 Design

This is a stratified Phase II study of escalating fractions of stereotactic body *radiotherapy* (SBRT) combined with immunotherapy for previously untreated or previously treated metastatic melanoma patients. Patients will undergo a short course of high dose SBRT to a single index lesion that is suitable for SBRT. These fractions will be administered several days apart. Radiotherapy will be immediately followed by ipilimumab, at the FDA-approved dose and schedule.

Stratified Phase II study: With safety data from an identical University of Pennsylvania study, SBRT fractions of two and three fractions has been shown to be safe. At UW/SCCA the Phase II study begins with Dose Level 1. If three fractions of SBRT are found to not be safe, the dose level will be reduced to Dose level -1 for the phase II portion of that stratum.

Stratification by Site of Index Lesion						
Dose Level	Stratum 1: bone or lung			Stratum 2: liver or subcutaneous		
	Dose per fraction	Fractions	# Patients	Dose per fraction	Fractions	# Patients
-1	8 Gy	2	6	6 Gy	2	6
1	8 Gy	3	6	6 Gy	3	6

The MTD has been defined by the Phase I trial at the University of Pennsylvania as 3 fractions of SBRT. The Phase II study can commence at UW/SCCA at dose level 1 (above). Patients will be treated at the MTD defined for their index lesion site. In Phase II, patients will be stratified by disease site: Stratum 1: phase 1 bone or lung and Stratum 2: phase 1 liver or subcutaneous. Stratum-specific response rates will be calculated. Enrollment will proceed independently for the

CONFIDENTIAL

This material is the property of the study sponsor. Do not disclose or use except as authorized in writing by the study sponsor

Printed on 1/31/2017

two strata. Forty total patients will be enrolled in this phase. Thus a maximum of 40 patients will be entered at the MTD. Twenty patients will be enrolled in each stratum

8.2 Objectives:

Phase II study: The primary objectives are to determine for each stratum, immune-related clinical response rate, immune-related progression-free survival rate at 6 months (irPFS6), and overall survival rate at 12 months (OS12). The secondary objectives are to gather additional data on acute and late toxicity and immune pharmacodynamic changes.

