8.3 Endpoints

Toxicity: CTCAE version 4.0 grades will be employed. Any patient who receives any amount of radiotherapy or study medication will be included in the toxicity analysis.

Dose-limiting toxicity (DLT) is defined generally as associated with the treatment, and for ipilimumab, that the event must be consistent with an immune-related effect. DLT is experienced during study treatment or within 30 days after last injection of ipilimumab, as long as the patient has not started another systemic treatment for cancer and is defined more precisely in Section 5.2.

Maximum tolerated SBRT fraction (MTD) is defined as the SBRT fraction dose level at which 0-1/6 patients experience DLT and at least 2 patients treated at the next higher dose level experience DLT (or the apparent MTD is Dose level 1).

Late toxicity is defined generally as an adverse event associated with the treatment which occurs beyond 30 days after last injection (i.e., adverse events which are observed months after treatment are most likely associated with SBRT) and is defined more precisely in Section 5.2.

Response: Immune-related clinical response will be scored on a non-index lesion using immune-related response criteria (irRC) according to irRECIST 1.1 (48). Patients who do not complete a clinical response evaluation, with the exception of those patients with rapidly progressing disease, will be scored as unevaluable. The immune-related clinical response rate is defined as the proportion of patients treated at the MTD who achieve either a complete or partial immune-related response. Unevaluable patients are included in denominator for the calculation of the objective response rate.

Immunologic outcomes include: 1) analysis of lymphocyte subsets and lymphocyte activation, 2) analysis of antigen-specific T cells and 3) tumor-specific T cells, as described in Section 7.2.2. For T cell response analyses, overall immune response is defined as >2 fold pre-treatment/post-treatment increase in any of the key T cell parameters.

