8.4 Plans for De-escalation

A DLT rate $\geq 33\%$ is considered unacceptable. Enrollment will proceed independently in the two strata. If a DLT is observed, then all subsequent patients will be treated at Dose Level -1.

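### The stopping sentence for dose level -1 (8.4.1) gives no DLT count, denominator or stratum; read literally it ends the whole study at 1 of 6, a result 8.3 accepts as the MTD

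*Combined protocol and SAP*

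**What the plan says.** The stopping rule for dose level -1 is in 8.4.1: "If DLTs are observed at dose level -1, this will cause termination of the study". No other section gives a count for that level or limits the stop to one stratum.

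The related provisions are:

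- **MTD (8.3):** "the SBRT fraction dose level at which 0-1/6 patients experience DLT", with the added condition that at least two patients at the next higher level had a DLT (or that the apparent MTD is level 1).
- **Unacceptable rate (8.4):** 33% or more. The same section has the two strata enrolling independently.
- **De-escalation from level 1:** 8.4.1 says "Two or more DLTs will cause de-escalation to Dose level -1, which will be the MTD". Section 8.4 says "If a DLT is observed, then all subsequent patients will be treated at Dose Level -1", and 6.2.3 says "If we encounter a dose limiting toxicity, we will then reduce our total dose to dose level -1".
- **Strata (8.1):** if three fractions prove unsafe, "the dose level will be reduced to Dose level -1 for the phase II portion of that stratum"; also "Patients will be treated at the MTD defined for their index lesion site".
- **Numbers:** the 8.1 table lists six patients per stratum at each level. The Study Summary says "In phase II, 20 patients will be treated at the MTD in each stratum". Sections 3.1 and 8.1 cap the trial at 40, with 20 per stratum. Sections 8.5 and 8.6 calculate with 14 patients per stratum.

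**The concern.** A stopping rule has to give one answer for each set of data, and this one does not. After 1/6 at level -1, a safety committee could declare the MTD under 8.3 or terminate under 8.4.1. After a second DLT well beyond the sixth patient, it could continue because the rate is far below 33%, or terminate because two DLTs have occurred.

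The scope is also open. Dose reduction, MTD and enrolment are handled by stratum, but the sentence ends the study. On its face, DLTs in liver or subcutaneous patients on two fractions would close enrolment for bone or lung patients who are tolerating three.

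The route into level -1 is contradictory as well. One DLT is enough in 8.4 and 6.2.3, whereas 8.4.1 responds to a first DLT by requiring follow-up of the remaining patients and de-escalates only at two. That is a separate defect, but it sits in the same set of rules and should be repaired with them.

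**Working it through.** **Inputs.** Six patients per stratum and level (8.1 table, 8.3); 20 per stratum (Study Summary, 8.1); 14 per stratum (8.5, 8.6); limit of 33% (8.4). The documents give no true DLT rate for either level, so 5%, 10%, 20% and 33% are assumptions. DLTs are treated as independent between patients.

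**1. The plan's own table (8.4.2).** The rule that passes a level with 0-1 DLT in 6 has probability (1-p)^6 + 6p(1-p)^5. At p = 0.40 this is 0.0467 + 0.1866 = 0.233; the table gives 0.23. For 10% to 90% the formula gives 0.886, 0.655, 0.420, 0.233, 0.109, 0.041, 0.011, 0.0016 and 0.0001, and all nine entries match. A conventional 3+3 rule would give 0.906, 0.709, 0.494 and 0.309 at 10% to 40%, and does not match. The quantified rule in the plan is therefore 2 or more of 6, which is 33% and agrees with 8.3 and 8.4.

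**2. Stopping within six patients at level -1.** P(any) = 1-(1-p)^6; P(exactly 1) = 6p(1-p)^5; P(2 or more) = P(any) - P(exactly 1). At p = 0.10: 1 - 0.531 = 0.469; 0.354; and 0.114 before rounding.

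| True rate | Any DLT | Exactly 1/6 | 2 or more |
|---|---|---|---|
| 5% | 0.265 | 0.232 | 0.033 |
| 10% | 0.469 | 0.354 | 0.114 |
| 20% | 0.738 | 0.393 | 0.345 |
| 33% | 0.910 | 0.267 | 0.642 |

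The middle column is the disputed outcome: a stop under the any-DLT reading, an acceptable MTD under 8.3.

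**3. Two or more, with no denominator.** How many patients can be treated at level -1 depends on whether level 1 patients use places in the 20. If only the two level 1 patients with DLTs do, 20 - 2 = 18 remain. If a cohort of six does, 20 - 6 = 14 remain. If none do, 20 remain.

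| Patients at level -1 | Lowest observed rate at a stop | P(stop), 5% | 10% | 20% |
|---|---|---|---|---|
| 14 | 2/14 = 14% | 0.153 | 0.415 | 0.802 |
| 18 | 2/18 = 11% | 0.226 | 0.550 | 0.901 |
| 20 | 2/20 = 10% | 0.264 | 0.608 | 0.931 |

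**4. How often the 1/6 conflict would arise.** Assume the same true rate at both levels and a level 1 trigger of 2 or more in 6, so that the second condition in 8.3 is met. The probability per stratum is P(2 or more of 6) × P(exactly 1 of 6). At 10% it is 0.114 × 0.354 = 0.040; at 5%, 0.033 × 0.232 = 0.008; at 20%, 0.345 × 0.393 = 0.136.

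**5. Scope.** If one stratum triggers termination, the other, judged on six level 1 patients at a 10% true rate, has 0-1 DLT with probability 0.886. In most such cases the stratum closed alongside would not have met its own de-escalation trigger.

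**The case against.** The best defence is that the intended rule can be recovered. The preceding sentence says two or more, the level -1 sentence uses the plural, the 8.1 table plans six patients at that level, and 2 of 6 is 33%. On that reading nothing conflicts in the first six patients. This is persuasive about intent and it points to the repair, but the sentence does not state it, and it leaves the denominator and the stratum open.

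Second, stopping early at the lowest dose protects patients and is a legitimate choice. That stands. The plan, however, neither declares the choice nor gives its operating characteristics, and 8.3 points the other way.

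Third, the situation is unlikely. That also stands. 8.1 and 8.4.1 report two and three fractions as safe in the earlier phase I trial, a DLT must be probably or definitely radiation-related (5.2), and oversight committees review stopping rules (10.2).

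Three stronger readings are tempting and are not supported:

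- A reader might infer that the one-DLT route in 8.4 and 6.2.3 makes the contradiction with 8.3 much more frequent. On that route level 1 has usually had only one DLT, so the condition in 8.3 of at least two at the higher level is mostly unmet, and stopping at 1/6 does not contradict it.
- A reader might take 2/20 as the settled figure. The Study Summary supports 20 at the MTD, but the cap of 20 per stratum leaves 18 or fewer once level 1 patients are counted.
- A reader might treat 33% as a running boundary that the plan has promised to observe through patient 20. Section 8.4 calls that rate unacceptable; it does not say to continue until it is reached.

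**Conclusion.** The rule is wrong as written. It can end the whole study on data that 8.3 accepts and that lie below the limit in 8.4, and its study-wide scope does not fit the stratum-level rules in 8.1 and 8.4. The one-versus-two DLT contradiction at level 1 is plain on the page and needs no calculation.

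The reading chosen matters once level -1 is reached: at 10%, the chance of stopping runs from 0.11 (two or more in six) to 0.47 (any DLT in six), and to between 0.42 and 0.61 for two or more with no denominator. Reaching the 1/6 conflict is uncommon, about 0.04 per stratum at 10% (0.01 to 0.14 over 5% to 20%). These figures rest on assumed true rates, equal at both levels for the 0.04, and on a 2-of-6 level 1 trigger.

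The documents do not show that a per-stratum stop was intended, only that the neighbouring rules work that way. Severity: minor to should-fix.

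**What to change.** 1. In 8.4.1, replace the level -1 sentence with: *if 2 or more of the first 6 patients at dose level -1 in a stratum have a DLT, that stratum closes; the other stratum continues under its own rule.*
2. In the level 1 paragraph of 8.4.1, make the MTD designation of level -1 conditional: it is the MTD for that stratum if 0-1 of 6 patients have a DLT.
3. Bring 8.4 and 6.2.3 into line with the two-DLT trigger in 8.4.1, by stratum and with a stated denominator.
4. Leave any monitoring boundary after the sixth patient to the sponsor. If one is adopted, add its operating characteristics to 8.4.2.
5. If an any-DLT or study-wide stop at level -1 is what the sponsor wants, state it and amend 8.1, 8.3 and 8.4.2 to match.

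The cost is amendment wording, plus a table row if a later boundary is added; items 1 to 3 need no extra patients or visits. The price is some conservatism: at a 33% true rate, the 2-of-6 rule stops by the sixth patient with probability 0.64, against 0.91 for the literal any-DLT rule. The sponsor should make that trade knowingly.

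### Section 8.4.1 gives two different SBRT prescriptions to a replacement for a Dose Level 1 patient who enrols after the stratum has de-escalated

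*Combined protocol and SAP*

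**What the plan says.** All patients start at the higher level. Section 8.4.1 states that "the initial dose level in this study will be Dose level 1 (3 fractions of SBRT").

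The replacement paragraph of Section 8.4.1 covers two groups:

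- Patients who leave for reasons unrelated to the study before any study therapy "may be replaced as required for the study to meet its objectives".
- Patients who have had study therapy but withdraw, for reasons other than toxicity, before the DLT observation period is complete "will not count toward dose escalation rules and may be replaced as required".

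The principal investigator decides on replacement. The paragraph ends: "The replacement will receive the same treatment or treatment sequence (as appropriate) as the allocation number replaced".

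The de-escalation text is in several places:

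- Section 8.4.1: "Two or more DLTs will cause de-escalation to Dose level -1, which will be the MTD", and then "If two or more DLTs are observed in Dose Level 1, then all subsequent patients will be treated at Dose Level -1".
- Section 8.1: "If three fractions of SBRT are found to not be safe, the dose level will be reduced to Dose level -1", a reduction that Section 8.1 confines to the stratum concerned.
- Section 8.4: "If a DLT is observed, then all subsequent patients will be treated at Dose Level -1". Section 6.2.3 likewise reduces the dose after a single DLT.

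**The concern.** A replacement enrolled after de-escalation is both a replacement and a subsequent patient, so both sentences in Section 8.4.1 apply. If the person replaced had been assigned Dose Level 1, one sentence points back to that level and the other to Dose Level -1. The patient would then have two SBRT prescriptions under one protocol. Read literally, the replacement sentence would treat a new patient at a level that the de-escalation rule had just closed because of toxicity. A treating team facing this case would have to choose between the sentences without guidance from the text.

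**Working it through.** The point is textual. The only arithmetic is the dose totals and a check on what can be said about frequency.

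**1. Dose totals** (dose per fraction and number of fractions from the Section 8.1 table; totals stated in Section 6.2.3)

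- Bone or lung: Dose Level 1 is 8 × 3 = 24 Gy; Dose Level -1 is 8 × 2 = 16 Gy.
- Liver or subcutaneous: Dose Level 1 is 6 × 3 = 18 Gy; Dose Level -1 is 6 × 2 = 12 Gy.

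The stated totals are reproduced. The levels differ by one fraction, 8 Gy or 6 Gy (24/16 = 18/12 = 1.5).

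**2. The two sentences applied to each case within a stratum**

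| Level of patient replaced | Replacement enrols | Replacement sentence gives | De-escalation sentence gives | Agree? |
|---|---|---|---|---|
| 1 | before de-escalation | 1 | 1 (not triggered) | yes |
| 1 | after de-escalation | 1 | -1 | **no** |
| -1 | after de-escalation | -1 | -1 | yes |

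**3. Can the conflicting case occur?** Yes. Enrolment starts at Dose Level 1, and both replaceable groups can include patients assigned to that level. Nothing requires a replacement to enrol before the stratum de-escalates.

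**4. Is precedence stated?** No. The words in parentheses in the replacement sentence qualify the choice between a treatment and a treatment sequence; they mention neither dose level nor de-escalation. Section 8.1 says that patients are treated at the MTD for their index-lesion site, and Section 8.4.1 makes Dose Level -1 the MTD after two DLTs. Those statements bear on the question, but neither mentions replacements.

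**5. What allocation number refers to.** The term appears only in this sentence. Section 4.3 issues a subject study number, and the trial is open label with no randomisation.

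**6. When the conflict begins.** Under Sections 6.2.3 and 8.4 a patient is subsequent after one DLT; under Section 8.4.1, after two. Between the first and second DLT, the documents therefore disagree on whether de-escalation has happened at all.

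**7. Frequency.** The nearest figure in the plan is the operating-characteristics table in Section 8.4.2, the chance of 0 or 1 DLT in 6 patients. At a true rate of 40% this is 0.6^6 + 6 × 0.4 × 0.6^5 = 0.0467 + 0.1866 = 0.233, printed as 0.23. The other entries also reproduce. The table says nothing about replacements.

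The documents give no expected DLT rate. With assumed true rates p and 20 evaluable patients in a stratum, all at Dose Level 1:

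- P(two or more DLTs) = 1 − (1−p)^20 − 20p(1−p)^19: 0.26 at 5%, 0.61 at 10%, 0.93 at 20%.
- P(one or more DLTs) = 1 − (1−p)^20: 0.64, 0.88 and 0.99.

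These figures cover the de-escalation step only. The conflict also needs a replaceable Dose Level 1 dropout, a decision to replace, and enrolment of the replacement after the change. The documents give no withdrawal rate, so the joint probability cannot be calculated.

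**The case against.** The strongest reply is that the case may never arise. Replacement is permitted only where required. For treated patients, the paragraph links it to their not counting toward the dose rules. Once two DLTs have settled Dose Level 1, another evaluable patient at that level is arguably not required. The MTD statements in Sections 8.1 and 8.4.1 also bear on how a replacement would be read, and the sentence looks like template wording carried over from an allocated design.

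Much of this stands as a limit on importance. It does not remove the conflict. Section 8.1 plans 20 patients per stratum, so a replacement may still be wanted to fill a place after de-escalation. The text neither forbids this nor names the level. Template origin would explain the sentence, but the sentence is still in force.

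Three stronger readings are tempting and are not supported:

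- *A reader might infer that every replacement after de-escalation has two prescriptions.* Only replacements of Dose Level 1 patients do.
- *A reader might infer that withdrawal and de-escalation will often overlap, because the DLT window is long.* With four injections at 3-week intervals it runs nominally 63 + 30 = 93 days from the first injection. That shows overlap is possible. With no withdrawal rate, it does not show that overlap is likely.
- *A reader might infer that the response-rate denominator becomes unclear.* Section 8.3 defines it as patients treated at the MTD, and Section 8.5 tables responses and toxicity by stratum and fraction dose level. A patient given the other level falls plainly outside the denominator.

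**Conclusion.** The inconsistency is real but narrow. It needs a replaced patient assigned to Dose Level 1, a stratum that has since de-escalated, and an investigator who chooses to replace. In that case Section 8.4.1 gives prescriptions that differ by one fraction (24 or 16 Gy; 18 or 12 Gy), and no section expressly says which applies. The conclusion rests on reading subsequent patients to include replacements, since no exemption is written, and on reading de-escalation by stratum, as Section 8.1 does.

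A reader might infer a serious design flaw because the subject is dose. The documents do not support that: the case is conditional, replacement is optional, its frequency cannot be estimated, and the analysis definitions are unaffected. It is a minor textual inconsistency, worth correcting because it sits in a dosing rule. The one-DLT versus two-DLT trigger is a separate inconsistency, but it determines when this one begins.

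**What to change.** - Reconcile the two sentences in Section 8.4.1 so that a replacement enrolled after a dose-level change has exactly one stated dose level.
- Remove the term allocation number, or define it in terms of the subject study number in Section 4.3.
- In the same edit, reconcile the de-escalation trigger across Sections 6.2.3, 8.4 and 8.4.1, so that the point at which a patient becomes subsequent is fixed.

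Which rule governs is for the sponsor and the safety reviewers to decide. The replacement wording costs one or two sentences in the next amendment. It adds no patients or procedures and leaves the analysis unchanged.
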